The aim of LANTERN project is to develop accurate predictive models for lung cancer patients, using different omics-based variables, integrating well established clinical factors with big data and advanced imaging

features. This technological solution will be able to capture patients' conditions at multiple levels, supporting an effective disease prevention and further reducing the healthcare costs through personalized treatments.

More specifically, we will develop Digital Human Avatars (DHA) defined as computerized representations of individual patients and their characteristics, with a specific focus on advanced biological functions, as well as relevant pathological variables, which will be modelled, sourced and parametrized in a cutting-edge experimental "big data" setting.

Secondary objectives

Our main goals are:

i. To gather information from all the clinical and omics-based data sources acknowledged as clinically significant

ii. To ensure an easy and effective omics data inter-actionability and to allow their complete integration into archiving systems

- iii. To set up dedicated multi-omics data models and create a comprehensive lung cancer DHA
- iv. To enable feedback data loops for preventive healthcare strategies and quality of life (QoL) management
- v. To ensure that all the potential stakeholders are involved in the DHA development process.

METHODOLOGY

This is a prospective observational study

WP1: Omics data collection

The five main omics data tiers that will be identified as the ontology of this project, reflecting all the involved omics domains in the lung-cancer decision making pathway are: A. Demographic and physiological data; B. Medical history, clinic-functional, laboratory data and treatment information; C. Histo-pathological, immunological and genetic data; D. Radiomics and quantitative imaging data; E. Internet of Things derived data.

A structured terminological system for prospective collection of anonymized data will be developed, creating a dedicated database for all omics domains considered. The data will be stored in a dedicated server and categorized according to the data reported in the WP1. Researchers will provide a structured terminological system for prospective collection of anonymized data in which all information will be recorded through specific Case Report Forms (CRFs), ensuring uniformity and consistency for all variables collected. Tumour

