Proposed radiomic analysis will be as follows: first, gross tumour volume (GTV) delineation will be performed retrospectively by experienced lung malignancy Radiotherapy Oncologists on each patient's images (CT images in DICOM (.dcm) format). DICOM files containing not only the CT images but also the RT structure file will be exported and processed using MODDICOM, an R package developed to optimize automatic loading of DICOM images and radiomic analysis. Radiomic features will then be extracted automatically. The extracted radiomic features belong to different families: Intensity-based, morphological, textural and fractal. All analyzed image features will be based on the standardization criteria of the IBSI initiative.

WP3: omics data modelling, avatar creation and knowledge transfer

Developing accurate predictive models and creating Digital Human Avatars (DHA) - Omics features identification and selection: In the first step, an exploratory analysis across all collected datasets (An estimate of \approx 240 NSCLC patients) will enable the start of the biomarker identification process and restrict the cast amount of information towards a more selected pool of potential biomarkers. This first phase will employ robust data analysis techniques in order to identify relevant variables (T3.1.) in a univariate setting, taking individual statistical distributions, feature-relevant correlations and general descriptive statistics into account.

Patient selection

INCLUSION CRITERIA:

- Patients with (suspected) NSCLC
- Age >18 yrs
- ECOG 0-3
- Written Informed Consent

EXCLUSION CRITERIA:

- ECOG 4
- Psychosocial, or emotional conditions controindicating participation to the study

STATISTICAL ANALYSIS METHODOLOGY

An estimate of 600 Patients (both male and female) with \geq 18 years of age with pathologically proven diagnosis of non-small cell lung cancer (NSCLC) will be enrolled. Sample size was calculated on the basis of G-powerR program for "a priori" analysis, considering α =5% and power of 90%.

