The Wilcoxon Mann-Whitney (WMW) test will be used to investigate the ability of these features to predict clinical outcomes on univariate analysis, and the feature showing the lowest p-value will be considered as the most predictive parameter. Receiver Operating Feature curve analysis (ROC) will also be performed on the most significant feature obtained at WMW analysis, calculating the area under the curve (AUC) with the corresponding 95% confidence interval (CI) according to the Clopper-Pearson method. Model processing will be performed through advanced ML and AI techniques first on a dedicated training dataset to fit the model parameters. The obtained hyperparameters will be tuned on a dedicated validation dataset and finally a test dataset will be employed as a dataset independent of the training dataset but following the same probability distribution.

Predictive model development

The objective of the second phase is creating multiple distinct but modular multivariate models, trained through advanced ML and AI techniques and segmented into specific modular areas of interest (T.3.2).

Different supervised models will be developed including logistic regression, decision tree, support vector machine, random forest, XGBoost classifier, and artificial neural networks. The k-fold cross-validation will be used for hyperparameters tuning. The final step in the proposed methodology is the statistical significance comparison of the performance of the ML models. This will be done evaluating predictive performances in terms of different metrics: the first evaluation will be based on accuracy (number of subjects correctly classified on the total number of patients) while the other will be on precision (true positive on total test positive), recall (sensitivity), F1 score (2*precision*recall/(precision+recall)) and AUC-ROC.

We estimate about 300 NSCLC cases with complete data to start developing the models. Specific care will be taken to always ensure both user friendliness and model explainability as primary pillars of the model development strategies. Easily interpretable values such as SHAP (SHapley Additive exPlanations) values will be attached to each model in order to avoid any black-box approaches that might render model outputs, difficult to explain to the patients during their interactions with the clinicians.

Predictive model validation

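### Candidates are narrowed one at a time, lowest WMW p-value is the only ranking named and no variable is protected, so rare or singly weak predictors can be lost before modelling

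*Combined protocol and SAP*

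**What the plan says.** In the WP3 section, the first step is exploratory and covers every collected dataset, on an estimated 240 patients. Its purpose is to cut the information down "towards a more selected pool of potential biomarkers". The method: "This first phase will employ robust data analysis techniques in order to identify relevant variables (T3.1.) in a univariate setting". Correlations, distributions and descriptive summaries are to be weighed as well, but how they are to be used is not stated.

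Under Statistical Analysis Methodology, the only test named is WMW, which "will be used to investigate the ability of these features to predict clinical outcomes on univariate analysis". The ranking rule follows: "the feature showing the lowest p-value will be considered as the most predictive parameter". That feature then goes to ROC analysis. Predictive model development describes the multivariable models as the second phase, with about 300 complete cases to start from.

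The main objective is to build models "integrating well established clinical factors with big data and advanced imaging". The data tiers in WP1 include "C. Histo-pathological, immunological and genetic data; D. Radiomics and quantitative imaging data; E. Internet of Things derived data", alongside demographic, clinical and laboratory data. The Abstract gives actionable mutations and PD-L1 expression as examples of what now makes treatment decisions complex.

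The document gives no p-value cut-off, no number of variables to keep, no list of variables kept whatever their result, no grouping of rare alterations and no handling of missing values in this step.

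**The concern.** A univariate p-value does not measure predictive value alone. It also depends on how common a feature is and in how many patients it was observed. A yes/no alteration carried by a few percent of patients can have a large odds ratio and still give an unremarkable p-value. So can a clinical factor that is weak alone but useful jointly, or one that is often missing. WMW also needs an ordering, and no test is named for nominal variables such as histological type.

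If the pool passed on is shaped by such a ranking, it tilts toward common, continuous, fully observed features, radiomics above all. A model cannot use a variable removed before fitting. At stake is whether the integrated models contain the genomic and clinical predictors they are meant to combine.

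**Working it through.** **Inputs from the document.** About 240 patients in the screening step (WP3), WMW as the test and lowest p-value as the ranking (Statistical Analysis Methodology), and about 300 complete cases for modelling (Predictive model development). The plan gives no operating figure for the screen, so there is none to reproduce. The total of 600 cannot be tied to this step, because neither an effect size nor a test is given for it.

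**Assumptions, not in the document.** Odds ratio (OR) 3 for a binary marker, outcome rate 30% or 50% in non-carriers, carrier prevalence 2–40%, two-sided 5% level.

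**Step 1: a rare marker, worked by hand.** Take 5% carriers and a 30% outcome rate in non-carriers.
- Outcome odds in carriers: 3 × 0.3/0.7 = 1.286, a rate of 0.5625.
- Overall outcome rate: 0.95 × 0.3 + 0.05 × 0.5625 = 0.3131, or 75.15 patients with and 164.85 without the outcome.
- Carriers among those with the outcome: 0.0281/0.3131 = 0.0898. Among those without: 0.0219/0.6869 = 0.0318. Difference 0.0580.
- AUC of the marker: 0.5 + 0.0580/2 = 0.529.
- For a binary feature, tie-corrected WMW is in effect a comparison of two proportions. Its standard error is √[0.05 × 0.95 × (1/75.15 + 1/164.85)] = 0.0303, so the expected z is 0.0580/0.0303 = 1.91.
- Power ≈ Φ(1.91 − 1.96) = 0.48.

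With a 50% outcome rate the same steps give a difference of 0.0475, standard error 0.0281, z = 1.69 and power 0.39.

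**Step 2: the range by simulation.** Tie-corrected WMW, 4,000 datasets per setting, n = 240, OR 3:

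| Carriers | Expected number | P(p<0.05), outcome rate 50% to 30% |
|---|---|---|
| 2% | 5 | 0.17–0.27 |
| 5% | 12 | 0.39–0.47 |
| 10% | 24 | 0.68–0.72 |
| 20% | 48 | 0.89–0.91 |
| 40% | 96 | 0.97–0.98 |

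**Step 3: comparison with a weaker continuous feature.** A fully observed continuous feature with only OR 1.5 per SD reaches p<0.05 in 0.79–0.84 of datasets. The 5% marker with OR 3 outranks it in only 17–28% of runs, and a 2% marker in 7–16%. A stronger rare marker does better: with OR 5 and 5% carriers the figure is 29–52%.

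**Step 4: number observed.** The power of that continuous feature falls to 0.63–0.71 with 30% of values missing and to 0.49–0.54 with 50% missing, its true effect unchanged.

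**Step 5: would ranking by AUC be better?** No. Take 240 patients, 5% carriers, OR 3 and a 40% outcome rate in non-carriers: the marker's true AUC is 0.526. For a continuous null feature, taking 40% of patients with the outcome, the standard deviation of the AUC is √[241/(12 × 240² × 0.4 × 0.6)] = 0.038. To be among the 10 most extreme of 300 null features needs |z| of about 2.13, an AUC near 0.5 + 2.13 × 0.038 = 0.581. In simulation the marker reaches the top 10 in about 38–40% of datasets by p-value and in about 0.1% or fewer by AUC. The tie-corrected test allows for prevalence, and AUC does not.

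**The case against.** The strongest objection is that no rule is written under which the WMW p-value decides entry to the models. The lowest p-value names one feature, which goes to ROC analysis. The exploratory step also looks at distributions and correlations. The words introducing the test refer to features without a clear antecedent and may mean the radiomic ones only. All of this stands. A reader might infer that variables are selected into the models by WMW p-value, and the document does not support that. What it does support is a univariate restriction before modelling, a single named test and ranking, and silence on the entry rule.

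Second, strong common factors are safe: OR 3 at 40% prevalence is detected in 97–98% of datasets, and OR 2 per SD in 99–100%. A reader might infer that established clinical factors as a class would be dropped, and the calculation does not bear that out.

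Third, the models are to be modular. If the modules follow the data tiers, which the document does not say, genomic variables need not compete with radiomic ones. That would ease the ranking problem in step 3 but not the low detection rates in step 2, which involve no competitor. Underperforming models may also be retrained with new specifications, but nothing says that screened-out variables would be reconsidered.

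Fourth, prevalence, odds ratio and outcome rate are assumptions, and the document gives no alteration frequencies. Its mention of low-frequency somatic variants should not be read as meaning variants rare among patients.

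**Conclusion.** The concern holds in limited form. The plan narrows variables univariately, names only WMW p-value ranking, states no entry rule and protects no variable, although its main objective depends on integrating established factors. The loss is plausible for rare alterations and for clinical factors that are weak alone, act jointly or are often missing. With OR 3 and an outcome rate of 30–50% in non-carriers, a 5% marker misses p<0.05 in about 53–61% of datasets of 240 and a 2% marker in about 73–83%. These figures show how a p<0.05 screen would behave. They do not predict what the investigators will do, because no cut-off is stated.

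A reader might go further and conclude that jointly acting features are certain to be lost, or that the main question will be answered with the wrong inputs. With the entry rule unwritten, the document supports neither. The change is worth making because it is cheap and affects which predictors the integrated models can use.

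**What to change.** In the WP3 section and under Statistical Analysis Methodology:

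1. Prespecify a core set (established clinical and pathological factors, PD-L1 and one pooled actionable-driver variable) kept in every integrated model whatever its univariate p-value.
2. Reduce only the high-dimensional continuous features, such as radiomics, without looking at outcome, by correlation clustering. Exempt genomic alterations from any near-zero-variance filter, which would remove the rare ones.
3. In place of the univariate screen, select among the remaining candidates by penalised multivariable regression grouped by tier, within the training data.
4. Keep WMW and single-feature ROC as descriptive, and delete the statement that the lowest p-value marks the most predictive parameter. Do not substitute a ranking of single features by AUC (step 5 of the working). Judge a tier by the change in out-of-sample performance of the multivariable model when it is added, in the same patients.

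The cost is protocol and SAP wording, modest coding on data already to be collected and a few extra terms per model, with no change in patient numbers. Pooling drivers loses which driver is present. Forced entry secures retention, not precision: 5% of 300 cases is 15 carriers, so individual rare alterations still need penalisation or grouping.

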Methodology: All necessary factors (clinical, epidemiological, technical, economic, organizational, social, legal and ethical implications) will be considered for the proper implementation of the DHA in healthcare. To

Protocol LANTERN_v1.0 del 16.12.2022

this aim, a robust and rigorous scientific methodology will be applied by combining quantitative approaches (collection of scientific evidence and systematic literature reviews/meta-analysis; consultation of institutional flows and databases/hospital discharge forms/national price lists and data analyses; mathematical models; cost-utility/budget impact analyses) and qualitative research techniques (Consensus conference, Focus group, Delphi, Expert opinion).

The LANTERN project is configured as highly innovative, since for the first time in the field of lung cancer research, we intend to develop a predictive platform powered by the integrated reading of data from the main omics sciences. The project has the ambition to combine data from radiomics with clinical and biological data, derived from biological omics (through the analysis of the patient's biological samples) on a digital platform. This project though seems ambiguous, has a well-thought out plan and is highly feasible through the cooperative work efforts and experience of each consortium partner in their respective fields. With the commitment of each partnering centre in undertaking their respective delegated tasks as described in the project work plans and tasks, We believe the LANTERN project will be completed within a timeframe of 3 years which aligns with the expected time taken for the project completion as stated in the call document.

Personalised medicine represents an evolution from traditional "one size fits all" strategies, extending the concept of stratifying cancer treatments on well-known clinical and pathological characteristics to a more individual, patients specific, truly personalized level. However, the current approach typically relies on molecular and cellular data-sets (i.e. mutations) that are very limited and relative only to subsets of the complex web of cellular data that determine treatment outcomes. Due to various histological, genetic, immunological and imaging characteristics that define its highly variable oncological outcomes, lung cancer represents an ideal case to run AI based multidimensional personalized medicine studies, thereby fitting into the purpose of this project.

AIMS

Main objectives

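### The feature labelled most predictive is chosen and scored without regard to stage, so it may reflect disease extent alone, and no planned analysis would show this

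*Combined protocol and SAP*

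**What the plan says.** **Who is enrolled.** Under Patient selection, the inclusion criteria are "Patients with (suspected) NSCLC", age, ECOG 0-3 and written consent. The exclusions are ECOG 4 and "Psychosocial, or emotional conditions controindicating participation to the study". The Statistical Analysis Methodology section adds pathological proof of NSCLC. None of these concerns stage, resectability or treatment intent.

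**How features are screened.** The WP3 section describes a first exploratory step on about 240 patients, carried out "in a univariate setting, taking individual statistical distributions, feature-relevant correlations and general descriptive statistics into account". Under Statistical Analysis Methodology, the WMW test "will be used to investigate the ability of these features to predict clinical outcomes on univariate analysis"; then "the feature showing the lowest p-value will be considered as the most predictive parameter". ROC analysis "will also be performed on the most significant feature obtained at WMW analysis", with an AUC and a confidence interval.

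**What the candidates include.** For radiomics, computed from the delineated gross tumour volume, the WP2 section says: "The extracted radiomic features belong to different families: Intensity-based, morphological, textural and fractal".

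**What the project is for.** The Summary of Project Rationale and Workplan describes personalised medicine as "extending the concept of stratifying cancer treatments on well-known clinical and pathological characteristics to a more individual, patients specific, truly personalized level".

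In the text available for review, tumour stage is not named as a covariate, stratum, subgroup, split variable or comparator.

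**The concern.** With no stated stage limit, the cohort may mix patients whose expected course differs widely. An unstratified test of feature against outcome compares all patients with the event to all without it. If events are concentrated in advanced disease, any feature that rises with stage will separate the two groups, even if it says nothing about two patients at the same stage. Morphological and intensity features of the delineated tumour are plausible candidates for this, although the plan does not say so.

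The interpretation of the result is at stake. A feature reported as the most predictive, with a respectable pooled AUC, would be read as new information. It could instead be a proxy for a characteristic clinicians already use, which is the grouping the project sets out to go beyond.

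**Working it through.** **Plan's own figures.** The plan gives no figure on this point. Its enrolment of 600 (alpha 5%, power 90%) cannot be reproduced, because the effect size, outcome and test are not stated; nothing below depends on it. From the plan I take n=240 at the screen, the WMW test and the lowest-p rule. Every other input is an assumption.

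**1. Pooled AUC of a pure stage marker.** Assume two equal stage groups with event rates e1 (early) and e2 (advanced), and a normal feature shifted by d SD between groups and unrelated to outcome within each. Pairs from the same group contribute 0.5. Hence

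AUC = 0.5 + (A − B) × [Φ(d/√2) − 0.5],

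where A is the probability that the event patient is advanced and the non-event patient early, and B is the reverse.

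- Events 20% vs 70%: A = (0.70/0.90) × (0.80/1.10) = 0.566; B = (0.20/0.90) × (0.30/1.10) = 0.061; A − B = 0.505.
  - d=1: 0.5 + 0.505 × 0.260 = 0.631.
  - d=0.5: 0.5 + 0.505 × 0.138 = 0.570.
- Events 30% vs 60%: A − B = 0.424 − 0.121 = 0.303.
  - d=1: 0.5 + 0.303 × 0.260 = 0.579.

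The within-stage AUC is 0.50 in every case.

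**2. How often the test is significant.** Each setting has 45% events, so 108 events and 132 non-events. The null SE of the AUC is √[241/(12 × 108 × 132)] = 0.0375, and power is roughly Φ[(AUC − 0.5)/0.0375 − 1.96]. Simulation (two separate sets of 3,000 runs, two-sided 5%) agrees:

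| Setting | Pooled AUC | Approximate power | Unstratified WMW, simulated | Stage-stratified (van Elteren), simulated |
|---|---|---|---|---|
| d=1, 20% vs 70% | 0.631 | 94% | 94.6-94.8% | 5.2-5.3% |
| d=0.5, 20% vs 70% | 0.570 | 46% | 45.4-47.3% | 4.9-5.0% |
| d=1, 30% vs 60% | 0.579 | 56% | 55.5-57.0% | 5.0-5.2% |

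**3. The plan's actual rule, lowest p.** Assume four stages mixed 30/15/25/30%. Event rates from stage I to IV are 25/35/45/55% (mild), 15/30/50/70% (moderate) or 10/25/55/85% (strong). The stage marker shifts by a fixed amount per stage and competes with one genuine feature (within-stage AUC 0.60) and 100 null features, at n=240 with 500 runs per setting.

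| Stage gradient | Shift per stage | Stage marker wins, unstratified | Stage marker wins, stratified |
|---|---|---|---|
| Mild | 0.5 SD | 15% | 0.6% |
| Mild | 1.0 SD | 42% | 0.6% |
| Moderate | 0.5 SD | 69% | 0.0% |
| Moderate | 1.0 SD | 99% | 0.2% |
| Strong | 0.5 SD | 94% | 0.8% |
| Strong | 1.0 SD | 99.8% | 0.2% |

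With a smaller shift of 0.25 SD per stage and the mild gradient, the pooled AUC is 0.541 and the unstratified test is significant in 20% of runs. Stratifying removes the stage marker but does not by itself find the genuine feature, which wins 26-44% of stratified contests.

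**4. Would a later step reveal it?** The test set is meant to follow the same distribution as the training set, so a stage proxy would perform equally well there. The validation split is described by location or time, not stage. The listed metrics (accuracy, precision, recall, F1, AUC) are given without a stage breakdown or a baseline model.

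**The case against.** Much of the opposing case stands.

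- **A reader might infer that all stages are enrolled.** The documents do not say so. They only set no limit, and the actual mix is unknown.
- **A reader might infer that performance will be reported for the whole cohort only.** The plan is silent on subgroups, and its models are divided into modular areas of interest that it does not define. Silence is not a commitment to pooled reporting.
- **A reader might infer that the avatar itself would be a stage proxy.** That does not follow. The screen is exploratory and is meant to yield a pool of candidates; nothing says that only the lowest-p feature goes forward. The Main objectives promise to integrate established clinical factors, and the data tiers include medical history, treatment and histopathology. If stage enters the multivariate models, a pure stage proxy adds nothing there. But the plan does not commit to stage as a predictor, and later adjustment does not correct the label or AUC already given to the selected feature.
- **The mechanism needs an outcome that depends on stage.** The plan says only clinical outcomes. The dependence is plausible for survival but not certain for every endpoint.
- **The size is illustrative.** The 95% comes from the strongest of three two-group settings, and a feature that is pure noise within stage is the worst case.
- **A pooled AUC is a valid target for prediction across all comers.** This is correct, and it is a reason not to discard the pooled screen: a purely stratified screen would change the selection target and could drop features useful for that purpose.

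**Conclusion.** The point holds in a limited form. As written, the plan can label as most predictive a feature that only tracks disease extent, report an AUC that does not show this, and carry out no specified analysis that would. That leaves the stated aim of going beyond known grouping untested.

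Under the two-group assumptions at n=240, a feature with no within-stage information reaches a pooled AUC of 0.57 to 0.63 and is significant in about 45% to 95% of runs, against about 5% when stratified. Under the lowest-p rule with four stages, it is selected in 15% to 99.8% of runs. These ranges rest on assumed stage mixes, event rates and feature shifts. They show that the risk can be large, not how often it will occur in this cohort. With a weak stage gradient it is possible but not the usual result.

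**What to change.** 1. Make pre-treatment stage group a required CRF variable, with the grouping fixed in the SAP before outcomes are analysed.
2. Keep the pooled WMW test and pooled AUC for all-comer prediction. Add a stage-stratified (van Elteren) p-value for each screened feature as a companion result.
3. For the selected feature and every final model, report the within-stage AUC beside the pooled one, using only event/non-event pairs from the same stage group.
4. Compare each final model with a baseline model containing stage and established clinical factors, on the same test data.
5. Base any claim of personalisation on the within-stage or incremental figure.

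The cost is SAP wording, one routine CRF field and a few lines of analysis; enrolment and treatment are unaffected. Reported AUCs will tend to be lower and within-stage intervals wider. In the 20% vs 70% example, same-stage pairs number 24 × 96 + 84 × 36 = 5,328 of 108 × 132 = 14,256 (37%). The null SE rises from 0.0375 to √(5,328 × 121/12)/5,328 = 0.0435, about 16% wider. More or smaller stage groups would widen it further.

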Both the developed model and the comprehensive DHA will be validated in order to test their robustness, transferability and generalizability. Two consecutive validation strategies will be employed respectively: the internal and external validation techniques. We estimate a total number of \approx 420 NSCLC cases to start the validation process. This process will include both internal and external validation. The internal validation step will be focused mainly on techniques such as K-fold cross validation. This will allow to achieve a Transparent Reporting of a multivariable prediction model for Individual Prognosis Or Diagnosis (TRIPOD) level 2b. At this TRIPOD level, data are non-randomly split (e.g., by location or time) into 2 groups: one to develop the prediction model and the remaining dataset to evaluate its predictive performance. In the case of suboptimal performances, all the failing models will be reverted back to the previous stage and the models will be retrained with new specifications in order to increase their robustness. At this point, the models can be validated using external datasets, reaching TRIPOD 3 and 4 levels (External validation). Finally, when the models reach a TRIPOD 4 level, data transferability and full actionability will be granted, allowing the successful and safe application of the model in the clinical Routine (T3.3).

ETHICAL CONSIDERATIONS

Considering the technicality and complexity of the LATERN Project, consortium partners are well aware of the various ethical and legal questions relating to the project. The main ethical issues related to this project include:

the respect for persons and for human dignity; fair distribution of benefits and burden; the rights and interests of the participants; the need to ensure participants' informed consent; processing of personal data; concerns involving the development, deployment and/or use of artificial intelligence (AI)-based systems or techniques.

Protocol LANTERN_v1.0 del 16.12.2022

Therefore, LATERN partners will identify and implement a comprehensive set of ethical and legal requirements in accordance with Declaration of Helsinki principles to ensure compliance for all activities of the project. Appropriate ethical monitoring systems will also be set up.

To this effect, LATERN will implement the following activities:

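### The AUC of the feature picked by lowest p-value has no stated separate patients or selection correction, and its Clopper-Pearson interval is not valid for an AUC

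*Combined protocol and SAP*

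**What the plan says.** Under the WP3 heading, the first step is "an exploratory analysis across all collected datasets", put at about 240 NSCLC patients, to "identify relevant variables (T3.1.) in a univariate setting". The statistical analysis section then tests features against clinical outcomes by WMW, and "the feature showing the lowest p-value will be considered as the most predictive parameter". ROC analysis "will also be performed on the most significant feature obtained at WMW analysis", giving an AUC with a 95% Clopper-Pearson interval.

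No other patients are named for this AUC, and no adjustment for choosing the best of many candidates is described. The number of candidates, the outcome and the event rate are not stated.

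The safeguards nearby are written for something else. The training, validation and test sets belong to model processing, where "a test dataset will be employed as a dataset independent of the training dataset". The validation section covers the developed model and the Digital Human Avatar, and there "The internal validation step will be focused mainly on techniques such as K-fold cross validation", followed by external validation. Neither mentions the single-feature AUC.

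**The concern.** The WMW statistic divided by the product of the two group sizes is the AUC. Without ties, ranking features by WMW p-value is therefore ranking them by distance of the AUC from 0.5. Choosing the smallest p-value and then reporting that feature's AUC from the same patients reports the largest of many noisy estimates as if it had been the only one. An ordinary 95% interval takes no account of the choice.

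At stake is a reported biomarker. A feature with little or no predictive value could be named most predictive and shown with a credible-looking AUC and an interval that misses its true value.

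A second, separate fault is the interval itself. Clopper-Pearson is built for a binomial proportion. An AUC averages over pairs of patients with and without the event, and its variance depends on both group sizes.

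**Working it through.** **Inputs.** From the plan: about 240 patients in the univariate step, selection by lowest WMW p-value, 95% Clopper-Pearson interval. The plan gives no AUC, interval width or optimism figure to reproduce. Assumed: 30% events (72 with, 168 without; 10% as a variant), 20, 100 or 500 candidates, normally distributed features, independent unless stated. Bias means the winner's reported AUC minus that feature's own true AUC.

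**Step 1: no signal, by formula.** The standard error of an AUC when nothing predicts is sqrt[(n+1)/(12·n1·n0)] = sqrt[241/(12·72·168)] = 0.0407. The expected largest |Z| among m independent standard normals, the integral over z > 0 of 1 − (2Φ(z) − 1)^m, is 2.17, 2.75 and 3.24 for m = 20, 100 and 500. The products are 0.088, 0.112 and 0.132, so the reported AUC would average about 0.59 to 0.63 when the truth is 0.50.

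**Step 2: simulation (bias at 240 patients, 30% events).**

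| True state | 20 features | 100 | 500 |
|---|---|---|---|
| None predicts | 0.09 | 0.11 | 0.13 |
| One at AUC 0.60 | 0.05 | 0.08-0.09 | 0.11-0.12 |
| One at 0.65 | 0.01 | 0.03 | 0.05 |
| One at 0.70 | about 0 | at most 0.01 | about 0.01 |

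The first row agrees with Step 1. With one feature at 0.60 among 100, a noise feature was named the winner in about 60% of runs.

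**Step 3: where the bias starts and stops.**
- Several equally good features: among 100 candidates with AUC 0.75 for each real one, the bias is about 0.04 with five and 0.06 with twenty. A strong signal does not remove it if the leaders are close together.
- Few events: with 24 events and one feature at 0.70, the bias is roughly 0.03 to 0.12 over 20 to 500 candidates. With one feature at 0.80 it is at most 0.02.
- Correlation: at 0.8 between features and no signal, the bias falls to about 0.06, 0.08 and 0.09 for 20, 100 and 500 candidates.

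**Step 4: the interval without any selection.** The plan names no denominator for Clopper-Pearson; take 240. At AUC 0.65 the binomial standard error is sqrt(0.65·0.35/240) = 0.031. The Hanley-McNeil standard error of an AUC is 0.040 with 72 events and 0.063 with 24. The binomial interval is too narrow in both cases. Simulated coverage for one pre-named feature is about 88-91% at 30% events and 70-73% at 10%. With denominator 72 the binomial standard error is sqrt(0.2275/72) = 0.056, which is too wide. Neither choice is right.

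**Step 5: the remedy.** With 100 candidates, no signal and the AUC taken in 360 separate patients (600 − 240), the mean AUC was 0.496, 0.500 and 0.499 for event rates of 10%, 20% and 50%. DeLong coverage was about 94-95%, against about 1% for DeLong in the screening patients. A valid interval alone therefore does not cure the selection. Ten-fold cross-validation with selection inside each fold gave 0.50-0.51 with no signal.

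**The case against.** The step is labelled exploratory, and the models face a test set and external validation. That stands as a limit on the consequence: no go/no-go rule uses this AUC, and external validation of the models is unaffected. It does not rescue the AUC, which the plan gives a definite label and a 95% interval.

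It is also fair that the plan never says the same patients are used. That is read from silence; no others are named for this step.

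Four stronger readings are tempting and should not be drawn.
- That the bias is always material. One clearly dominant feature is reported almost without bias.
- That few events alone cause it, or that a strong signal always prevents it. Step 3 contradicts both.
- That all undercoverage comes from selection. Part is the Clopper-Pearson method, as Step 4 shows.
- That the models' internal performance is inflated because screening patients reappear in it. The plan says "We estimate about 300 NSCLC cases with complete data to start developing the models" and puts about 420 "NSCLC cases to start the validation process", but it does not say whether these counts include the 240, whether the WMW result decides what enters the models, or whether screening is repeated within folds. Development in one TRIPOD 2b group could naturally include feature selection. This remains a question for the sponsor, and no size can be attached to it.

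**Conclusion.** The point holds as a reporting flaw that should be fixed. On the plain reading, the named feature's AUC is optimistic whenever the best signal is weak relative to the number of candidates and events, or the leading features are nearly tied. Under the assumptions used, that is about 0.09-0.13 with nothing predictive, 0.05-0.12 at a true AUC of 0.60, 0.01-0.05 at 0.65, at most 0.01 at 0.70, and about 0.04-0.06 with five to twenty equal features at 0.75. The direction follows from the selection rule. The size cannot be fixed from the documents, because it rests on assumed feature counts, event rates and independence. The wrong interval method is a separate fault that remains even if the selection problem is solved.

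**What to change.** - Report the selected feature's AUC and interval from patients not used to select it, or its AUC from cross-validation with the WMW selection repeated in every training fold. Bootstrap optimism correction is a weaker choice: it left 0.53-0.54 when the truth was 0.50.
- Label the AUC in the screening patients as apparent.
- Replace Clopper-Pearson with an interval valid for an AUC, such as DeLong or a bootstrap interval.
- State whether the 240, 300 and 420 are cumulative and whether the WMW result decides what enters the models. If it does, fix the test dataset and the TRIPOD 2b evaluation group before any outcome-based screening, and repeat the screening inside each training fold. Outcome-blind steps may use all patients.

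The cost is wording and computing time, with no extra enrolment. The reported AUC will probably be lower. Precision depends on how many patients are held out: at AUC 0.65 and 30% events, the Hanley-McNeil half-width is 0.08 with 240 patients, 0.11 with 120 (420 − 300, if cumulative) and 0.06 with 360. If the 240 are the first enrolled, 360 is a ceiling. The work plan runs enrolment to month 30 and WP3 to month 32, so late patients may have no outcome in time.
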